	Claims study for whitening efficacy of NextGen whitening technology
	Clinical Endpoint: Oral Soft and hard tissue Assessment, Safety and Whitening
	improvements.

10. Washout Products with PDM/Substance Numbers:

Dundunt	PDM/Substance #	If Applicable Sample
Product	(or link to pdm)	Description
N/A		

11. Test Products with PDM/Substance Numbers:

		If Applicable		
Product	PDM/Substance # (or link to pdm)	Sample Description	Product Code	
Colgate Cavity Protection Toothpaste	200000056803/002/000	Study Supply	N/A	
Colgate Adult Extra Clean soft-bristle toothbrush	461000000452	Study Supply	N/A	
Philips Zoom Professional Whitening Treatment	30000006549/000/000	Control - Light-Activated Whitening - 25% HP gel for in-office use only	Blinded Product	
Opalescence Boost PF	30000006551/000/000	Control - 40%HP whitening gel for in-office use only	Blinded Product	
Beaming White + Gingival Barrier + CP LED	30000006550/000/000 30000006732/000/000 461000003779	Test - 25%HP gel for in- office use only Gingival Barrier CP LED 20mA	Blinded Product	

SYNOPSIS

U.S.1RB Study Title: Clinical Study to Evaluate the Tooth Whitening Efficacy of a new NextGen in-office system

Principal Investigator:

[name], DMD

President/Owner Consumer Research Consulting, LLC

[name]

e. [contact]

m. [contact]

Examiner: [name], DMD

[name] Study Location/Country:

Study Phase: Phase III

Study Products Included for the Clinical Trial:

Group (#subjects)	Study Products	Arm
60	Beaming White - 25%HP Gel + Gingival Barrier + CP LED	Test
60	Philips Zoom Chairside Light-Activated Whitening System - 25% HP Gel	Positive Control
60	Opalescence Boost PF - 40%HP Gel	Positive Control

Objective: To evaluate the Clinical efficacy of a NextGen in-office whitening system compared to commercially available in-office whitening systems.

Study Parameters:

Single-Center Number of centers: Parallel

Design: Examiner-blind **Blinding:**

Randomization (RCT) **Product assignment:** 180 male and female Number of subjects:

Subject's age group: 18 to 70 years old

Three (3) **Number of test products:**

In-office whitening application Treatment Regimen:

Number of Exposures (uses):

Screening/Baseline, immediately post-whitening, Day 7 Time-points:

Approximately one week **Duration of Study:**

45-60 minutes, depending on product assignment **Duration of each Exposure:**

None Washout period: On-site brushing: Yes

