Inclusion Criteria

Potential subjects must meet ALL of the following criteria:

- 1. Signed Informed Consent Form
- Male and female subjects aged 18-70 years, inclusive; 2.
- Good general health and good oral health based on the opinion of the study 3. investigator;
- All maxillary natural anterior teeth (teeth #6 through #11) must be present; 4.
- 5. Availability for the duration of the study;
- Minimum average Vita Extended Bleachedguide 3D-Master 6. shade score of 17 ≥ or darker.

Exclusion Criteria

Potential subjects must **NOT HAVE ANY** of the following conditions:

- Presence of orthodontic appliances and/or any anterior tooth with a prosthetic 1. crown, veneer, or deemed non-vital:
- Obvious signs of periodontal disease, rampant caries, or any condition that the dental examiner considers exclusionary from the study.
- Five or more carious lesions requiring immediate care. 3.
- Concurrent participation in another oral clinical study. 4.
- Self-reported pregnant and/or lactating women.
- History of allergies or sensitivity to tooth whitening products, hydrogen peroxide, personal 6. care consumer products, or their ingredients;
 - Restorations on the teeth to be scored which may interfere with scoring procedures.
- Have used professional whitening products within one (1) year and/or had dental 8. prophylaxis (professional dental cleaning) within thirty (30) days prior to the start of the study.

III. STUDY DESIGN

1. Configuration

This randomized, examiner-blind, single-center clinical study features a three-cell, parallel-group design to explore the use of a new in-office whitening technology compared to two existing technologies. Patients will be randomized to one of three study groups, and will undergo in-office whitening treatments according to their assigned group.

2. Duration

Subjects' participation in the study will consist of two (2) visits to the clinical research site during approximately 7 days duration of the study: Screening/Baseline, Day 7.

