All subjects will be evaluated visually for tooth color shades and conditions of oral tissues at the screening visit. If qualified, subjects will be enrolled and randomized into the study. Baseline visit will be performed on the same day, if time allows. All voluntary candidates will be evaluated for tooth color shades at study entry and the initial tooth shade scores will be recorded as baseline. All qualified subjects will be randomly assigned following a computer-generated master randomization list (online software Sealed Envelope Ltd v.2022) to one of the four treatment groups. Subjects will undergo in-office whitening treatment according to their assigned group. Afterwards, subjects will again have their tooth shade evaluated and recorded, and will be given instructions and hygiene products to use at home, and dismissed. In a subset of subjects (approximately 5/cell), extraoral photos will be taken prior to product application, and after all whitening sessions are completed.

The subjects will be asked to return to the clinic after 1 week, and will again be evaluated for tooth shade, conditions of oral tissues and the occurrence of adverse reactions. Images will again be taken, and a brief questionnaire will be completed to document the patient's experience. After this point, the subject will be dismissed from the study.

3. Master Randomization Plan

Qualifying participants (enrolled) will be randomized using an online software provided by Sealed Envelope Ltd. v.2022. This software employs a block randomization approach with a block size of 6 to ensure balanced allocation to the treatment groups. The randomization sequence will be pre-generated using the 'Create a blocked randomization list' tool. The computer-generated Master Randomization List, which contains random product codes, will be provided to the clinical site prior to the initiation of the study.

Protocol No: CRO-2 Table I. Study		MS	U.S. IRE OCT - 7 2025 *APROVED"
	Visit 1a	Visit 1b	Visit 2
Visit Procedure	Screening/ Baseline	Immediately after treatment	Day 7
Informed Consent Form/ Privacy Notice	х		
Medical History/Oral Health Questionnaire	Х		
Visit Form			x
Review Selection Criteria	Х		
Oral Soft and Hard Tissue Assessment	X	X	X
On-site brushing*	Х	X	X
Tooth Color Exam (Visual grading)	X	x	X
Photos (in subset only)	X	X	x
In-office whitening	х		
Questionnaire	х	X	X
Randomization, product assignment and instructions	X		

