4. Extraoral Photos

For the same subset of subjects, a final photo will be taken after whitening is completed, using the same techniques as before (with retractor in place, and no gingival barrier).

5. Questionnaire

Subject and provider will complete the relevant portions of a short questionnaire.

6. Study Product Distribution:

All subjects enrolled in the study will be provided with a soft-bristled adult toothbrush and toothpaste for home use. Subjects will be instructed to brush their teeth twice daily (morning and evening) for two (2) minutes each time with the toothpaste and toothbrush provided. All subjects will be instructed to repeat the same procedure twice daily for the duration of this study.

7. Instruction to Subjects

Subjects will be instructed to use only the products (toothpaste and toothbrush) provided during the study period, and to refrain from using any other oral hygiene products and from routine dental treatment (except emergency) during the course of the study. Subjects who receive dental treatment and/or use medication must report this to the study investigators. The use of tooth whitening products is prohibited. There will be no restrictions regarding diet during the course of the study. Subjects will be asked to return to the clinical facility 1 week post-treatment for subsequent clinical examinations.

Example of Label Instruction for both test and control groups (Appendix XI):

CRO-2025-09-WHT-MS

Product (Letter Code)

Brush your teeth twice daily (morning and evening) for two (2) minutes each time. Cover the entire length of the bristled head with toothpaste. Do not swallow. For investigational use only by the study participant. Not for Retail Sale. For Adult Use Only. Keep out of reach of children under 6 years.

In case of emergency or for further information telephone:

[name] at [contact]

Visits 2: (7 days +/- 3 days after Baseline):

1. Visit Form

After 7 days of study product use at home, all subjects will report back to the clinical site for their follow-up appointment. The study examiner will complete a Study Visit Form (Appendix IX) to account for health updates and/or adverse reactions.

2. Subsequent Oral Soft and Hard Tissue Assessment

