Study products will be supplied by the sponsor for this study. The study investigator will verify that the quantity of supplies, protocol number, and identification numbers match the information on the shipping invoice, and will store and account for the study supplies as described below.

Study Products Storage, Handling, and Accountability

The study products must be stored in a secure area with limited access, at room temperature. The investigator is directly responsible for the accountability of all used and unused study products. The investigator and all sub-investigators will make every effort to remain blinded as to the subject regimen. Records must be maintained to document the receipt and disposition of all study drug supplies provided to the investigator by the sponsor. The study monitor will review these records periodically during the course of the study. At the end of the study, or as directed by the monitor, the investigator must return all unused study products to the sponsor.

XIV. CONCOMITANT THERAPY

If a subject takes concomitant medications as a matter of necessity for the treatment of a medical condition, then such medication may be permitted for the duration of the study at the discretion of the investigator. However, it is the responsibility of the investigator to disqualify from entering the study any subject who, upon screening, is using medication or consumer products that might obscure the interpretation of study results. All medications currently used by the subject at enrollment, or any time through the end of the study, will be recorded on medical history and visit form. Subjects may receive medication to treat adverse events as deemed necessary by the investigator or the subject's physician.

XV. ADVERSE EVENTS

A. DEFINITIONS:

Adverse Events (AEs) and Serious Adverse Events (SAEs) are defined by the ICH Guideline for Good Clinical Practice (ICH GCP) as follows:

U.S. 1R8

Adverse Event: Any untoward medical occurrence in a patient or clinical investigations subject administered a pharmaceutical product and which does not necessarily have to have a causal relationship with this treatment. An adverse event (AE) can therefore be any unfavorable and unintended sign (including abnormal laboratory finding), symptom, or disease temporally associated with the use of a medicinal product, whether or not considered related to the medicinal product.

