APPENDIX V

Do you have a history of allergies to any oral care products, personal care consumer products, or their ingredients?

If yes, please fi	ll explain:		
Do y List any p	you take any med prescription or ove	ications? If yes	s, please fill out following: edications which you are taking:
Name of Medication	Amount taken	How often	Reason
	1		
	D	ENTAL HIST	TORY
Name of your o	dentist:		Phone#:
He	ow often do you vi	sit your Dentis	t?
	Date of	of last visit:	
		WOMEN ON	LY
	Plea	se answer the fo	ollowing:
Ara vou r	vragnant? V	N If was	list due data
Are you p			list due date;;;
-	, 1	,	
also understand to responsibility to in	hat this information form this office of	n will be held in fany changes in	day is correct to the best of my knowledge n the strictest of confidence, and it is my n my medical status. I understand that my
participation on this s	tudy is voluntary a	nd that I termir	nate my participation in the study at any tin
-	Signature		Date

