APPENDIX VI INITIAL SCREENING FORM

OCT	1	7	2025
-----	---	---	------

PAPROVED"

Subje	ct Number:	Subject Initials:	_ Gender [] M	[] F A g	ge:	
3. 4.	1. Signed Inform 2. Male and fem All maxillary anterio without the presence Average VITA Exter or darker for 6 maxill	ned Consent Form hale subjects, aged 18-70, in r teeth must be present; of crowns/restorations haded BleachedGuide 3D-Ma	clusive aster shade of 17	YES_	YES N YES N NO NO YES N	OV
If ansv	ver to any of questions lestion 14 below comple	1-5 is No, subject is ineligible eted. If subject is eligible, co	e for study. Subjections	ct should s 6-13.	d be dismiss	ed
6.7.	Obvious signs of perior any condition that exclusionary from the 8. Five or more	odontal disease, rampant ca the dental examiner consider	aries, ers mediate care.		_ NO NO YESN	
	10. Self-reported	pregnant and/or lactating w	omen.		YES N	1 O
11.12.13.	hydrogen peroxide, p products, or their ing Restorations on the te with scoring procedu Have used profession and/or had a dental pr	eeth to be scored which may	n one (1) year ntal cleaning)	YES_	NO NO	
If anso	wer to any of question ssed and Question 14	ns 6-13 is YES, subject is i completed.	neligible for stud	y. Subj	ect should	be
	14. IS SUBJECT	ELIGIBLE FOR ENTRY I	NTO THE STUD	Υ?	YES N	10
SIGN	ATURE EXAMINING	G DENTIST	DATE:			

U.S.IRA

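### The listed exclusions bar recent professional whitening but not a recently completed over-the-counter peroxide course, and no legible form item would reveal one

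*Combined protocol and SAP*

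**What the plan says.** - **Section II, exclusion 8.** It excludes those who "Have used professional whitening products within one (1) year and/or had dental" prophylaxis within thirty days, both counted back from the start of the study. The word professional limits the rule: exclusion 6 in the same list, on allergy and sensitivity, refers to tooth whitening products in general.
- **Appendix VI, Initial Screening Form.** The matching line is broken in the available text ("Have used profession and/or had a dental pr"), but what can be read repeats the professional restriction. No separate over-the-counter item is legible.
- **Synopsis.** The washout entry reads, with its labels run together, "None Washout period: On-site brushing: Yes". Washout products are listed as not applicable.
- **Section III, Duration.** "Baseline visit will be performed on the same day, if time allows". Table I places screening, baseline, randomisation and whitening all in Visit 1a.
- **Section II, inclusion 6.** The average must be a "shade score of 17 ≥ or darker". Section V also requires each of the six teeth to score at least 17.
- **Section V, Visit 1b, Instruction to Subjects.** "The use of tooth whitening products is prohibited". The instruction is given after treatment and applies from then on.
- **Section XIV.** The investigator must disqualify anyone who, "upon screening, is using medication or consumer products that might obscure the interpretation of study results".
- **Appendix V.** The legible product-history question is "Do you have a history of allergies to any oral care products, personal care consumer products, or their ingredients". It asks about allergy, not about whitening use.
- **Section VII.** Within-arm change is tested by paired t-test against baseline. Arms are compared by ANCOVA on shade change, with baseline shade as covariate.

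**The concern.** The plan accepts that earlier treatment of the teeth can affect the shade outcome. It excludes professional whitening for a year and a dental cleaning for thirty days, and it bans every whitening product once the subject is treated. Yet a home peroxide course that ended shortly before screening is not addressed. With no washout, no run-in and no repeat reading before treatment, nothing in the schedule would show whether such a subject's shade was still moving.

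Two things are at stake. The within-arm changes, which the paired t-tests assess and which a claims study may quote, would for these subjects start from a shade that has already been bleached. In addition, subjects with and without recent home whitening may respond differently, which would add variance to the between-arm comparison. If the history is not recorded, neither effect can be examined afterwards.

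**Working it through.** The plan states no figure on this point, so the main check is of the text.

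**Step 1: apply the rules to two candidates, each with all six teeth at 17 or darker.**

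| Rule | Cleaning three weeks ago | Over-the-counter peroxide course finished last week |
|---|---|---|
| Inclusion 6 and the per-tooth floor | passes | passes |
| Exclusion 8 | excluded (21 days is less than 30) | not covered |
| Exclusion 2 (examiner's judgement) | not needed | possible, but whitening is not named |
| Section XIV | not relevant | not literally covered, as use has ended |
| On-study ban | not relevant | starts only after treatment |

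The second candidate meets every listed criterion. Section V enters the first 180 subjects who meet the criteria and complete the forms, so the listed criteria carry the decision unless someone uses discretion.

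**Step 2: would discretion be informed?** It requires knowing the history. The legible parts of Appendices V and VI ask about allergies, medications and professional whitening, but not about home whitening.

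**Step 3: which analyses are exposed?** Prior use is a pre-randomisation characteristic, so its expected distribution is the same in each arm and the expected between-arm bias is zero. ANCOVA adjusts for the level of baseline shade, not for whitening history. The within-arm paired t-tests have no such protection.

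**Step 4: scale, on assumptions only.** The documents give no SD, effect size, power or prevalence.

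- Completers: 180 × 0.9 = 162, or 54 per arm. (Section II prints eighteen expected completers, which does not fit its own 10% drop-out, so the percentage is used.)
- Reference difference at 80% power, two-sided 0.05, normal approximation: (1.96 + 0.84) × √(2/54) = 0.54 SD.
- Assume that a share f of subjects are recent home whiteners and that their shade change is shifted by s SD equally in every arm. Take f from 0.05 to 0.20 and s from 0.5 to 1.5.
- Shift in each within-arm mean: f × s. From 0.05 × 0.5 = 0.025 SD to 0.20 × 1.5 = 0.30 SD.
- SD inflation: √(1 + f(1 − f)s²). From √(1 + 0.0475 × 0.25) = 1.006 to √(1 + 0.16 × 2.25) = 1.166.
- Power at 0.54 SD: from 80.1% without such subjects to 79.7% at the mild end and 67.2% at the extreme end. A middle case (f = 0.10, s = 1.0) gives 76.7%.
- Standard error of the between-arm difference due to chance imbalance in such users: s × √(2f(1 − f)/54). From 0.021 to 0.115 SD, centred on zero.

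These are unadjusted figures. If baseline shade is correlated with prior use, ANCOVA would recover part of the loss.

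**The case against.** The strongest reply is that entry is not automatic. Section XIV plainly covers anyone still whitening at screening. Exclusion 2 lets the examiner reject any condition judged unsuitable. The floor of 17 removes candidates already lightened past it. All of this stands, and it narrows the gap to completed use in someone still at 17 or darker whom nobody has excluded by discretion.

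It can also be said that the study's objective is comparative, and that randomisation with baseline-adjusted ANCOVA protects that comparison from expected bias. That is correct. A further defence is that admitting past home users is a pragmatic choice. It may be, but the plan does not say so, and its own exclusions point the other way.

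Appendix V is headed as a sample and its text is visibly broken, so the absence of a whitening question can be claimed only for what is legible.

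Three stronger readings are tempting, and the documents support none of them:

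- **That such subjects must be relapsing in shade or responding poorly to peroxide.** Someone who began much darker on the 29-tab scale could have responded well, be stable, and still score 17 or darker. No rebound data are given.
- **That differences between the systems would be diluted.** This needs the between-system difference to be smaller in prior users, and nothing in the documents supports such an interaction. A shift common to all arms leaves the expected difference unchanged.
- **That the one-year rule should carry over to home products.** The documents offer no basis for choosing that length.

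**Conclusion.** The gap is real but narrow. As written, a candidate who has recently completed an over-the-counter peroxide course and still scores 17 or darker meets all listed criteria, while one cleaned three weeks ago does not. This is inconsistent with the plan's own precautions, and no legible form item would bring the history to light.

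The expected between-arm bias is zero. What remains is avoidable between-subject variance and a qualification to the within-arm changes from baseline. The size cannot be derived from the documents. On the assumed ranges above it runs from almost nothing to a noticeable loss of power, and if few such users enrol it may be negligible. That a bleached baseline differs from a natural one for this purpose is an inference from the plan's own professional-whitening exclusion and on-study ban, not from data in the documents. This is a cheap improvement, not a flaw that threatens the main comparison.

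**What to change.** Three small edits:

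1. Extend exclusion 8 to over-the-counter peroxide-containing whitening products, within a look-back that the sponsor states and justifies. The plan's own look-backs, thirty days and one year, are the available reference points. Keep the present anchor, which counts back from the start of the study.
2. Make the same change to the matching item in Appendix VI.
3. Add one question to Appendix V asking which whitening products the candidate has used and when they were last used.

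If the sponsor prefers to admit past home users, the plan should say so. The Appendix V question alone would still allow them to be described by arm and examined in a sensitivity analysis.

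The cost is one criterion, one form line and one question, with no added visit or procedure. The downside is some additional screen failures and a slightly narrower study population.
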